4.4 Risks and Benefits

The subjects will not obtain any direct benefit from participation. Conducting this study may help identify new benefits of the Optimizer implant on arrhythmia burden and as a result help patients with AF in the future.

There are no physical risks related given the nature of this study and the fact that all procedures took place as per standard of care. The only foreseeable risk is related to breach of confidentiality since data is accessed for research purposes. All measures will be taken to minimize this risk and data will be stored in a coded manner and only de-identified data will be shared across institutions (see details in section 6).

5 – Methods

5.1 Sample Size Justification

The sample size is based on a statistical test of whether AF burden is reduced after Optimizer implant compared to the pre-implant period. We assume median pre-Optimizer implant AF burden of approximately 25%, which may be a conservative estimate given similar or higher reported device-monitored AF burden over 24 weeks in a genetically-defined group of heart failure patients (6). We hypothesize a 20% change in post-Optimizer AF burden (5% absolute reduction). The sample size calculation is based on a non-parametric Wilcoxon signed-rank test of the paired change in pre-Optimizer to post-Optimizer AF burden. Assuming a mean reduction of 5% and a standard deviation of 15% for the paired change in AF burden, alpha of 0.05 and power of 0.8, the required sample size is 77 patients. This sample size provides power >0.8 for a paired t-test. Based on a missing data rate of up to approximately 20% (e.g. due to dropout or unavailable device AF burden data), we plan to include up to 15 more subjects for a total of up to 92 subjects per arm.

The sample was calculated using PASS (Kaysville, UT) 2022 software.

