4.2.1 Number of Participants

We would like to evaluate up to 200 subjects from up to 50 subsites.

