5.2 Analysis Population

All patients identified and enrolled will be included in the analyses.

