5.3.1 Statistical Methods for Primary Objective

Primary Objective: The primary objective for both the retrospective and prospective arms of the study is to compare the AF burden noted 6 months pre Optimizer implant to 6 post Optimizer months (post Optimizer months 3-8), after 2 month blanking period

A patient's AF burden is measured as the cumulative time spent in AF over the assessment period divided by the cumulative follow-up time of the assessment period. The difference in AF burden between the post-Optimizer and pre-Optimizer AF assessment periods will be analyzed as a continuous variable. Visual inspection of q-q plots for skewness and outliers along with the Shapiro-Wilk test ($p>0.05$ indicates no deviation from normality and $p<0.05$ indicates deviation from normality) will be used to evaluate normality. If the distribution of changes in AF burden is approximately normally distributed, a paired t-test will be used for analysis and the mean, standard deviation, and range will be reported. Otherwise, if the distribution is non-normal, a Wilcoxon signed-rank test will be performed and the median, interquartile range, and range will be reported.

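### In section 5.1, 92 subjects per arm preserve the required 77 only up to about 16% missing data, not the stated 20%

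*Combined protocol and SAP*

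**What the plan says.** Section 5.1 (Sample Size Justification) sets the size from a paired comparison: "The sample size calculation is based on a non-parametric Wilcoxon signed-rank test". The inputs are a mean reduction of 5 percentage points in AF burden, a standard deviation of 15 points for the paired change, alpha 0.05 and power 0.8. The result is that "the required sample size is 77 patients". The allowance for losses follows: "Based on a missing data rate of up to approximately 20" percent, with dropout and unavailable device data as examples, "we plan to include up to 15 more subjects for a total of up to 92 subjects per arm". No inflation formula is given, and no other section states a different missing-data rate or a different number per arm.

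Three other sections bear on the point. Section 5.2 says "All patients identified and enrolled will be included in the analyses". Section 5.3.1 chooses the primary test from the data: "If the distribution of changes in AF burden is approximately normally distributed, a paired t-test will be used for analysis"; otherwise, "if the distribution is non-normal, a Wilcoxon signed-rank test will be performed". Section 4.2.1 sets the overall ceiling: "We would like to evaluate up to 200 subjects from up to 50 subsites".

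**The concern.** A missing-data rate normally refers to the patients enrolled. To keep 77 evaluable when a fraction m of those enrolled is lost, enrolment must be 77/(1 − m). Adding a fraction m of 77 gives too few, because the added subjects are themselves subject to loss. The 92 in section 5.1 looks like the second calculation.

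At stake is what the sentence tells its readers. The IRB, the sites and anyone tracking data completeness would take 92 per arm as securing the required number up to 20% missing. At 18% missing, for example, they would believe the 77 were safe, when 92 × 0.82 = 75.4. The power claim tied to 77 would then not be met for the test on which the sizing is based.

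**Working it through.** **Inputs.** From section 5.1: mean paired change 5, SD 15 (standardised effect 5/15 = 0.333), alpha 0.05, power 0.80, required n 77, missing data up to about 20%, 15 added, 92 per arm. From section 5.3: two-sided tests. From section 4.2.1: at most 200 subjects.

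**Step 1: reproduce the 77.** For the two-sided paired t-test, power comes from the noncentral t distribution with n − 1 degrees of freedom and noncentrality 0.333 × √n. The smallest n with power of at least 0.80 is 73 (power 0.802). The asymptotic relative efficiency (ARE) of the Wilcoxon signed-rank test to the t-test under normality is 3/π, so the Wilcoxon needs 73 × π/3 = 76.4, rounded up to 77. The plan's figure is reproduced.

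**Step 2: check the inflation.**

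- Evaluable from 92 at 20% missing: 92 × 0.80 = 73.6, so 73 to 74. Shortfall against 77: 3 to 4.
- Largest missing rate at which 92 still yields 77: (92 − 77)/92 = 15/92 = 16.3%.
- Enrolment that keeps 77 at 20% missing: 77/0.80 = 96.25, so 97 (97 × 0.80 = 77.6). That is 97 − 92 = 5 more per arm.
- Probable origin of 92: 77 × 1.20 = 92.4; equivalently 15/77 = 19.5%. This is inferred, since the plan does not show its formula.
- Totals: 2 × 92 = 184 and 2 × 97 = 194, both within 200.

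**Step 3: effect on power.** The t-test column uses the noncentral t as in step 1. The Wilcoxon ARE column uses the same formula with n replaced by 3n/π. The simulated Wilcoxon column gives the range from two simulations of 40,000 runs each, with changes drawn from a normal distribution with mean 5 and SD 15 (Monte Carlo standard error 0.002). The last column simulates the section 5.3.1 rule in 40,000 runs: t-test if Shapiro-Wilk p > 0.05, otherwise Wilcoxon. The q-q plot inspection cannot be simulated and is left out.

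| Evaluable n | Paired t-test | Wilcoxon, ARE | Wilcoxon, simulated | 5.3.1 rule, simulated |
|---|---|---|---|---|
| 73 | 0.802 | 0.783 | 0.783 to 0.785 | 0.803 |
| 74 | 0.808 | 0.789 | 0.788 to 0.790 | 0.806 |
| 77 | 0.823 | 0.805 | 0.805 to 0.808 | 0.821 |

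Under these normal changes the 5.3.1 rule selected the t-test in about 95% of runs, which is why its power tracks the t-test column.

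**Step 4: sensitivity to the SD.** By the ARE method, Wilcoxon power returns to 0.80 if the SD of the paired change is 14.69 (at n = 73) or 14.79 (at n = 74) instead of 15.

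**The case against.** The strongest reply is that a patient with missing data need not be lost to the primary analysis. Section 5.3.1 defines AF burden as time in AF divided by follow-up time in the period and sets no minimum follow-up. Someone who drops out in month 5 can therefore still supply a post-implant value. The pre-implant value is an eligibility condition, and section 5.2 includes everyone enrolled. At 20% missing about 18 of 92 are affected; if 3 or 4 of them had a usable partial period, 77 would be retained. This stands to the extent that 73 to 74 is the count when every patient with missing data lacks a paired change. It does not rescue the sentence. Section 5.1 itself treats missing data as subjects to be replaced, the paired change needs a value from both periods, no imputation is described, and nothing says how many patients would have partial data.

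A second reply is that the wording is approximate and 15/77 = 19.5% is close to 20%. That explains how 92 arose, but 15 of 77 is not the share of enrolled patients who can be lost. The stated upper end is about 20% and the cover ends at 16.3%.

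A third reply is that the planned analysis hardly suffers, and this largely stands. With normal changes the 5.3.1 rule keeps power at 0.80 to 0.81 even at 73 to 74, and an SD slightly below 15 would close the Wilcoxon gap. It limits the importance of the point, not its correctness.

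**Conclusion.** The figure is wrong as written, and the error is minor. The stated rate, the number per arm and the required 77 cannot all hold: 92 per arm covers about 16% missing data, and at 20% the shortfall is 3 to 4 evaluable patients, or 5 enrolled, per arm. That arithmetic assumes only that the rate applies to those enrolled and that missing data means no paired change, which is how section 5.1 uses it.

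The power figures rest on more: the plan's mean and SD, and normally distributed changes. On that basis the sizing test falls from about 0.80 to 0.81 to between 0.78 and 0.79, and the paired t-test stays at 0.80 to 0.81. Power under non-normal changes was not computed, because the plan gives no distribution for them. None of this shows a study that is materially underpowered.

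**What to change.** Reword the last part of the sample-size paragraph in section 5.1 in one of two ways.

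1. Keep 92 per arm and state that this covers about 16% missing data. This is the simpler choice, because it needs no distributional assumption.
2. Keep 20% and state that about 73 to 74 patients per arm would then be evaluable, with Wilcoxon power of about 0.78 to 0.79 and paired t-test power of about 0.80 to 0.81, both under normally distributed changes. That condition should be written into the sentence.

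Either costs one sentence and leaves 92 per arm and the 200-subject cap as they are; the stated cover or the stated Wilcoxon power becomes slightly less favourable. If the sponsor would rather have full cover at 20%, the matching number is 97 per arm, 194 in total, still under the cap but at the cost of up to 10 more subjects. Whichever is chosen, the inflation formula should be shown.

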5.2 Analysis Population

All patients identified and enrolled will be included in the analyses.

5.3 Statistical Methods

Descriptive statistics will be calculated for patient characteristics [age, gender (female/male), race/ethnicity (American Indian or Alaska Native, Asian, Black or African American, Hispanic, Native Hawaiian or Other Pacific Islander, White), body-mass index, presence of comorbid conditions (asthma, cancer, chronic obstructive pulmonary disease, coronary artery disease, diabetes mellitus, renal insufficiency, stroke), prior rhythm controlling strategies for AF or VT (antiarrhythmics, cardioversion, catheter ablation)]. For continuous variables, visual inspection of q-q plots for skewness and outliers along with the Shapiro-Wilk test ($p>0.05$ indicates no deviation from normality and $p<0.05$ indicates deviation from normality) will be used to evaluate normality or normal continuous variables, the mean, standard deviation, and range will be calculated. For non-normal continuous variables, the median, interquartile range, and range will be calculated. For categorical variables, counts and percentages will be reported.

| | |
|--------------|------------|
| Study Number | 12/20/2022 |
|--------------|------------|

All statistical analyses will be performed using SAS 9.4 (SAS Institute Inc., Cary, NC). All hypothesis tests will be two-sided with significance level $\alpha=0.05$. Any p-value below 0.05 will be deemed statistically significant.

5.3.1 Statistical Methods for Primary Objective

Primary Objective: The primary objective for both the retrospective and prospective arms of the study is to compare the AF burden noted 6 months pre Optimizer implant to 6 post Optimizer months (post Optimizer months 3-8), after 2 month blanking period

A patient's AF burden is measured as the cumulative time spent in AF over the assessment period divided by the cumulative follow-up time of the assessment period. The difference in AF burden between the post-Optimizer and pre-Optimizer AF assessment periods will be analyzed as a continuous variable. Visual inspection of q-q plots for skewness and outliers along with the Shapiro-Wilk test ($p>0.05$ indicates no deviation from normality and $p<0.05$ indicates deviation from normality) will be used to evaluate normality. If the distribution of changes in AF burden is approximately normally distributed, a paired t-test will be used for analysis and the mean, standard deviation, and range will be reported. Otherwise, if the distribution is non-normal, a Wilcoxon signed-rank test will be performed and the median, interquartile range, and range will be reported.

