A patient's AF burden is measured as the cumulative time spent in AF over the assessment period divided by the cumulative follow-up time of the assessment period. The difference in AF burden between the post-Optimizer and pre-Optimizer AF assessment periods will be analyzed as a continuous variable. Visual inspection of q-q plots for skewness and outliers along with the Shapiro-Wilk test ($p>0.05$ indicates no deviation from normality and $p<0.05$ indicates deviation from normality) will be used to evaluate normality. If the distribution of changes in AF burden is approximately normally distributed, a paired t-test will be used for analysis and the mean, standard deviation, and range will be reported. Otherwise, if the distribution is non-normal, a Wilcoxon signed-rank test will be performed and the median, interquartile range, and range will be reported.

VA episode counts will be tabulated for the pre-Optimizer and post-Optimizer assessment periods. A Poisson generalized estimating equation (GEE) analysis accounting for clustering of paired counts within subject may be performed to compare the rate of VA episodes between the pre-Optimizer and post-Optimizer assessment periods.

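### The outcome data choose both the primary test and whether a mean or a median change in AF burden is reported, so arms and looks may report different quantities

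*Combined protocol and SAP*

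**What the plan says.** Section 5.3.1 analyses each patient's post-minus-pre change in AF burden. Normality is judged by "Visual inspection of q-q plots for skewness and outliers along with the Shapiro-Wilk test", with 0.05 as the cut-off for the test. The result decides two things at once:

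- Judged normal: "a paired t-test will be used for analysis and the mean, standard deviation, and range will be reported".
- Judged non-normal: "Otherwise, if the distribution is non-normal, a Wilcoxon signed-rank test will be performed", and the summary becomes the median with its interquartile range.

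Section 5.3.2 repeats the rule for the exploratory AF burden comparisons: "If the distribution of changes in AF burden is approximately normally distributed, a paired t-test will be used".

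In section 5.1, "The sample size calculation is based on a non-parametric Wilcoxon signed-rank test of the paired change". The planning effect, however, is a mean: "Assuming a mean reduction of 5% and a standard deviation of 15% for the paired change in AF burden". The result is "alpha of 0.05 and power of 0.8, the required sample size is 77 patients". The same section adds that this number also gives power above 0.8 for a paired t-test, and it sets enrolment per arm.

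The primary objective is stated for both arms. Section 5.4 applies the primary methods descriptively each time 25 more patients have complete data and plans no early stopping. Section 6.6 allows interim results to be published.

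**The concern.** The two branches differ in more than the p-value. They report different quantities, and when changes are skewed the mean and the median are different numbers. Which one becomes the primary result is unknown until the outcomes have been seen. It depends partly on a visual reading, and the plan does not say whether the plot or the test prevails when they conflict.

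The design makes this choice repeatedly: once per arm, if the primary analysis is run by arm as the per-arm sizing implies, and again at each look. Shapiro-Wilk gains power as the sample grows, so the branch can change between looks although the population has not. A reader could be given a mean for one arm and a median for the other, or a median in the final report after a mean in an interim publication. Neither could be set cleanly against the other, and a median could not be set cleanly against the planned mean reduction of 5 points.

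**Working it through.** **1. The plan's own figure.** Inputs from section 5.1: mean change 5, SD 15, alpha 0.05 (two-sided by section 5.3), power 0.80.

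- Standardised effect: 5/15 = 0.333. By the noncentral t distribution the paired t-test needs n = 73 (power 0.802).
- Wilcoxon efficiency relative to the t-test under normality is 3/π, so n = 73 × π/3 = 76.4, rounded up to 77. This matches the plan.
- At n = 77 the t-test has power 0.823. For Wilcoxon the effective n is 77 × 3/π = 73.5, giving power 0.805.

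Both power statements in section 5.1 are therefore correct for normal changes.

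**2. How often two arms take different branches.** Let q be the chance that Shapiro-Wilk gives p < 0.05. For two independent arms of 77 with the same distribution, P(different branches) = 2q(1 − q). Only the Shapiro-Wilk part was simulated, because a visual reading cannot be. The documents do not give the shape of the change, so each shape below is an assumption, scaled to mean −5 and SD 15 (4,000 replicates). The skewed shapes have their long tail towards large reductions.

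| Shape | q | 2q(1 − q) | Mean | Median | Tests disagree on significance |
|---|---|---|---|---|---|
| Normal | 0.05 | 0.10 | −5.0 | −5.0 | 4% |
| t, 10 df | 0.19 | 0.31 | −5.0 | −5.0 | 5% |
| t, 5 df | 0.49 | 0.50 | −5.0 | −5.0 | 8% |
| Skewness 0.5 | 0.32 | 0.43 | −5.0 | −3.8 | 12% |
| Skewness 1 | 0.89 | 0.20 | −5.0 | −2.6 | 24% |
| Laplace | 0.70 | 0.42 | −5.0 | −5.0 | 10% |

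**3. A model of burden itself.** Patient means follow a beta distribution. Pre- and post-implant burdens are beta with concentration 12, and each patient's expected burden falls by exactly 20%. Section 4.2.3 requires pre-implant burden of 1–99%, so simulated patients outside that range are dropped.

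- Patient means beta(0.8, 1.8), eligible patients only: q is 0.17–0.18, so the arms differ in 2 × 0.17 × 0.83 = 0.28 to 2 × 0.18 × 0.82 = 0.30. The reported effect averages about −5.0 (median, when the test rejects) or −7.1 (mean, when it does not). The tests disagree on significance in 2%.
- Patient means beta(0.8, 2.2), which gives a median eligible pre-implant burden of about 25%, as section 5.1 assumes: q is about 0.222, so the arms differ in 2 × 0.222 × 0.778 = 0.345. The reported effect averages about −4.5 (median) or −6.4 to −6.5 (mean). The tests disagree in 3%.

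The criterion matters. Without it the first model gives q = 0.45 and arms differing in about half of trials, but about 12% of those simulated patients would not be eligible.

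**4. Looks.** In one accumulating sample viewed at 25, 50 and 75 patients, the branch changes at least once with probability 0.10 (normal), 0.23 (t, 10 df), 0.33 (skewness 0.5), 0.37 (t, 5 df) or 0.48 (Laplace). With skewness 0.5, q rises from 0.13 at 25 to 0.22 at 50 and 0.32 at 77.

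**5. Type I error of the switching rule** (n = 77, mean change zero): 0.05–0.055 for symmetric shapes and 0.064 for skewness 0.5. In that skewed case Wilcoxon alone gives 0.066, so the excess comes from Wilcoxon not being a test of the mean rather than from the preliminary test.

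**6. Power at 77 under skew.**

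| Shape | t-test | Wilcoxon | Switching rule |
|---|---|---|---|
| Skewness 0.5 | 0.84 | 0.72 | 0.78 |
| Skewness 1 | 0.85 | 0.61 | 0.63 |

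**The case against.** The strongest defence is that both tests and both summaries are written down in advance, both are adequately powered at 77 under the stated assumptions, and type I error hardly moves. All of that stands. What is not specified is which branch applies when the plot and the test point different ways, and which effect measure is primary.

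A second defence is that the gap is not created by the preliminary test. Mean and median differ in any skewed sample, and the switch only decides which is printed. This is largely right, and it is why always reporting both removes most of the harm. It does not make one of them the pre-specified primary result.

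Third, the looks are descriptive with no stopping decision, and no test of one arm against the other is planned. So only presentation and interpretation are affected. But the looks follow the primary methods and may be published, and readers will set the arms side by side.

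A reader might go further and infer that the trial is underpowered because it was sized for Wilcoxon alone. The documents do not support this: section 5.1 also covers the t-test, and its statement is correct. Nor do they support a claim that the arms would diverge in half of trials as a general result. That figure needs particular shapes, or a burden model that ignores the eligibility range.

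**Conclusion.** The concern holds as a point about the reported quantity and its comparability across arms and looks. It should be fixed, but it does not invalidate the trial.

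Its size depends on a distribution that the plan does not give. With skewed burden limited to eligible patients, the arms take different branches in about 28–35% of trials, and the branch moves the reported effect by about 2 points against a planned 5. The two tests reach different significance verdicts in only 2–3% of those samples. Across the other shapes, arm disagreement runs from about 10% (normal) to 50% (t with 5 df). For symmetric shapes the branch does not shift the expected estimate. All these figures treat Shapiro-Wilk as the sole criterion; the unscripted q-q reading adds discretion that cannot be quantified.

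Serious type I inflation is another tempting inference from data-driven test selection. The calculated rates, at most 0.064, do not bear it out.

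**What to change.** In sections 5.3.1 and 5.3.2, delete the normality-based switch and name one test for change in AF burden, to be used in both arms and at every look. Either choice is defensible: Wilcoxon signed-rank is the basis of the 77, and the paired t-test matches the planning effect, which is a mean reduction of 5 points. Keep the other as a sensitivity analysis. Whatever the distribution, always report the mean change and the Hodges-Lehmann (or median) change, each with a 95% confidence interval. Keep the q-q plot as description only.

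The cost is SAP wording; no patients are added. The choice of test does have a price that should be disclosed when it is made. If Wilcoxon is named, power at 77 is about 0.81 against 0.82 for the t-test when changes are normal. It can fall to about 0.72–0.61, against 0.84–0.85 for the t-test, if changes have skewness of 0.5–1 towards large reductions. With symmetric heavy tails the order reverses (t with 5 df: Wilcoxon 0.88, t-test 0.82).
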